17.3 Statistical Methods

All statistical processing will be performed using SAS[®] unless otherwise stated. Summary tables (descriptive statistics and/or frequency tables) will be provided for baseline variables, efficacy variables, and safety variables. Continuous variables will be described by descriptive statistics (n, mean, standard deviation, CV%, minimum, median, and maximum). Frequency counts and percentage of subjects within each category are provided for categorical data. Summaries will be provided for each treatment group.

The Safety set will include all subjects who received at least one application of the test article. The ITT set will include all randomized subjects. The PP set will be a subset of the ITT set and will include subjects who completed the study without any significant protocol deviations. The analysis of safety will be conducted on the Safety set. The analysis of efficacy will be conducted on both the ITT and PP sets, with the ITT set considered as the primary set for statistical analysis. Multiple imputation will be used to impute missing values for the primary endpoints and absolute change in total lesions count (S1) in the ITT analyses. Sensitivity analyses will be performed to investigate the robustness of the results obtained on the ITT set for the primary endpoints (change from Baseline in non-inflammatory and inflammatory lesion counts and IGA “success” at Week 12). Missing values for the other secondary endpoints (i.e., S2-S4: percent change in lesions counts) will be calculated using the values obtained from the multiple imputation of the primary efficacy endpoints and secondary efficacy endpoint #1 (S1).

17.3.1 Efficacy Analyses

17.3.1.1 Primary Efficacy Analysis

Hypothesis tests on the primary endpoints will be conducted in hierarchical order for P1 through P3.

P1: A logistic regression model with treatment and analysis center as fixed effects will be used to compare the proportion of subjects achieving “success” in each treatment group at Week 12, where “success” is defined as an IGA score of “clear” (score=0) or “almost clear” (score=1) AND at least a two-point improvement in IGA compared to Baseline.

P2: An analysis of covariance (ANCOVA) will be used to compare the absolute change from Baseline in non-inflammatory lesion count in each treatment group at Week 12, with treatment and analysis center as fixed effects and the Baseline non-inflammatory lesion count as the covariate.

P3: An ANCOVA will be used to compare the absolute change from Baseline in inflammatory lesion count in each treatment group at Week 12, with treatment and analysis center as fixed effects and the Baseline inflammatory lesion count as the covariate.

17.3.1.2 Secondary Efficacy Analysis

Hypothesis tests on the secondary endpoints will be conducted in hierarchical order for S1 through S4.

S1: An ANCOVA will be used to compare the absolute change from Baseline in total lesion counts in each treatment group at Week 12, with treatment and analysis center as fixed effects and the Baseline total lesion count as the covariate.

S2: An ANCOVA will be used to compare the percent change from Baseline in total lesion counts in each treatment group at Week 12, with treatment and analysis center as fixed effects and the Baseline total lesion count as the covariate.

S3: An ANCOVA will be used to compare the percent change from Baseline in non-inflammatory lesion counts in each treatment group at Week 12, with treatment and analysis center as fixed effects and the Baseline non-inflammatory lesion count as the covariate.

S4: An ANCOVA will be used to compare the percent change from Baseline in inflammatory lesion counts in each treatment group at Week 12, with treatment and analysis center as fixed effects and the Baseline inflammatory lesion count as the covariate.

17.3.1.3 Imputation of Missing Data

Missing values for the primary endpoint in the ITT analyses will be imputed by

- Multiple imputation using missing at random assumption;
- Missing at worst value (for the entire set);
- Worst case;
- Last observation carried forward; and
- Baseline observation carried forward.

17.3.1.4 Sensitivity Analyses

Sensitivity analyses will be performed to investigate the robustness of the results obtained on the ITT set for the primary endpoints. The first sensitivity analysis will be the Per Protocol analysis. Four additional sensitivity analyses will be performed using different methods of imputation on the ITT set. On a per-subject basis, missing values for the primary endpoints will be imputed with the

- 1) Worst value (for the entire set);
- 2) Worst case;
- 3) Last observation carried forward; and
- 4) Baseline observation carried forward.

17.3.1.5 Multicenter Studies

Each center will conduct the clinical study under a common protocol. Consistency in study execution at each center will be emphasized. The study is to be conducted in such a manner as to have a minimum of eight ITT subjects enrolled in each of the treatment groups at each center (i.e., 16 ITT subjects enrolled overall per study center). In the event

that there are too few subjects in a treatment arm for a center, then this center's data will be combined with another center's data in order to achieve the desired minimum number of subjects per treatment arm. The combining of data across centers will be accomplished by combining data from two or more centers based on geographical and climatic similarities until the minimum number of subjects per treatment arm is achieved. The sequence of combination will be based on the total number of subjects enrolled in each center (combining the lowest with second lowest and so on). Combining center data to achieve sufficient subjects per treatment arm will result in combined centers. These combined centers, as well as individual centers with sufficient subjects per treatment arm, will be referred to as "analysis centers" in the statistical analysis.

17.3.1.6 Multiple Comparisons/Multiplicity

All the hypothesis tests for the primary endpoints have to be performed at the same significance level $\alpha=0.05$ two-sided and the failure to reject a null hypothesis will imply the failure of rejecting of all the subsequent null hypotheses. This approach inflates the overall type II error β , which in the worst case scenario is equal to the sum of the Type II error β connected with the individual hypothesis tests.

The hypothesis test for the secondary endpoints will be performed at the same significance level $\alpha=0.05$ two-sided of the primary endpoints if and only if all the null hypotheses on the primary endpoints are rejected.

17.3.1.7 Subgroup Analyses

No subgroup analyses are planned.

17.3.2 *Treatment Compliance and Extent of Exposure Analyses*

17.3.2.1 Treatment Compliance

Compliance to the test article will be evaluated at each visit and overall according to the following formula:

$$100 \times \frac{\text{Number of actual applications}}{\text{Number of scheduled applications}}$$

Non-compliance will be defined as a compliance value less than 80%.

Descriptive statistics will be used to summarize test article compliance at each visit and overall for the ITT and PP sets. The proportion of compliant and non-compliant subjects will be summarized by table of frequencies at each visit and overall for the ITT and PP sets. Subjects with an overall compliance not evaluable (due to missing data) or less than 80% will be excluded from the PP set.

17.3.2.2 Extent of Exposure

Descriptive statistics will be used to summarize exposure to test article for the ITT, PP and Safety sets. The total amount of test article used (grams applied) will be calculated for each subject from the weights of the returned test articles. The mean daily amount of test article applied (total amount of test article used/number of days of treatment) will be calculated for each subject and summarized by treatment using descriptive statistics.

17.3.3 *Safety Analyses*

17.3.3.1 Local Skin Reactions (LSRs)

LSRs (telangiectasia, skin atrophy, striae rubrae, erythema, edema, scaling/dryness, stinging/burning, and pruritus) will be summarized by the frequency of each individual LSR by treatment group and severity at each visit.

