9.1 Visit 1 (Day 1): Screening/Baseline

Subjects can be screened for the study up to 45 days before Visit 1. During screening, the study requirements will be reviewed, written informed consent/assent obtained, and eligibility confirmed. If applicable, the washout from prohibited medications or treatments will be determined and implemented. Subjects who require "washout" for longer than 45 days will be re-consented.

At Screening, the investigator or designee will:

- Obtain a signed, written informed consent (unless the subject signed a consent within the past 45 days). Note: a subject under 18 years of age must provide written informed assent and be accompanied by the parent or legal guardian at the time of assent/consent signing. The parent or legal guardian must provide informed consent for the subject. If a subject becomes 18 years of age during the study, the subject must provide written informed consent at that time to continue study participation.
- Complete review and documentation of the subject's medical and dermatological history and demographic information.
- Record any concomitant medications and therapies.
- Confirm the subject meets the inclusion/exclusion criteria.
- Have subject complete washout from any prohibited medications, if necessary.

Once the Screening procedures have been completed, the investigator or designee will:

- Perform a dermatologic exam and brief physical exam (including vital signs, height, and weight).
- Perform a Fitzpatrick Skin Type assessment (see Section 10.3).
- Perform a UPT for all WOCBP (see Section 5.1.1 for definition). The results must be negative for the subject to be enrolled into the study.
- Perform an ECG.
- Perform IGA (see Section 10.1) and acne lesion counts (see Section 10.2) prior to the first application of the test article.
- Record Baseline LSRs (prior to application of the test article) (see Section 10.4).
- Perform photography for all subjects at all sites (see Section 11).
- If the subject meets the inclusion/exclusion criteria, randomize the subject to the next available (lowest) subject number.
- Weigh and dispense initial tube(s) of test article.
- Complete the Study Medication Accountability Log.
- Dispense the Subject Instruction Sheet to the subject and parent/guardian (if applicable) (Appendix 1).
- Dispense the Subject Diary (Appendix 2) to the subject and parent/guardian (if applicable) and provide completion instructions.

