- Instruct the subject and parent/guardian (if applicable) where and how to apply the initial dose of test article to the acne lesions on the face following the procedures in Section 6.2. The first application should occur in the office under supervision of the study staff.
- Record any AEs and LSRs (see Section 10.4) after the initial application of the test article.
- Instruct the subject and parent/guardian (if applicable) to apply the test article (about 1 gram) to the whole face twice per day, with at least eight (8) hours between applications.
- Update the Screening and Enrollment Log.
- Schedule Visit 2 (Week 4).

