10.4 Local Skin Reactions (LSRs)

At every study visit, the investigator or designee will document the severity of the following LSRs known to be associated with application of topical steroids:

- Telangiectasia
- Skin atrophy
- Striae rubrae

A five-point ordinal scale will be used to assess the severity of these reactions (0 = none, 1 = trace, 2 = mild, 3 = moderate, and 4 = severe).

In addition, the investigator or designee will evaluate the severity of the following LSRs known to be associated with acne vulgaris, using the five-point ordinal scales described below:

- Erythema
- Edema
- Scaling/dryness

Erythema:

0	None
1	Minimal – barely perceptible erythema
2	Mild – predominantly minimal erythema (pink) in the treated area with or without a few isolated areas of more intense erythema
3	Moderate – predominantly moderate erythema (red) in the treated area with or without a few isolated areas of intense erythema (bright red)
4	Severe – predominantly intense erythema (bright red) in the treated area with or without a few isolated areas of very intense (fiery red) erythema

Edema:

0	None
1	Minimal – scant, rare edema
2	Mild – easily seen edema, minimally palpable, involving up to 1/3 of the Treatment Area
3	Moderate – easily seen edema and typically palpable, involving between 1/3 to 2/3 of the Treatment Area
4	Severe – easily seen edema, indurated in some areas, involving over 2/3 of the Treatment Area

Scaling/dryness:

0	None
1	Minimal – barely perceptible desquamation
2	Mild - limited areas of fine desquamation in up to 1/3 of the treatment area
3	Moderate – fine desquamation involving 1/3 to 2/3 of the treatment area or limited areas of coarser scaling
4	Severe – coarser scaling involving more than 2/3 of the treatment area or limited areas of very coarse scaling

In addition, subjects will be asked to rate the severity of the following LSRS that occurred in the treatment area since the last visit, using the four-point ordinal scales described below:

- Stinging/burning
- Pruritus

Stinging/burning:

0	None
1	Minimal, barely perceptible – tolerable and little discomfort
2	Moderate – tolerable, but causes some discomfort
3	Severe – very uncomfortable or intolerable

Pruritus (itching):

0	None - no evidence of itching
1	Mild - only aware of itching at times, only present when relaxing, not present when focused on other activities
2	Moderate - often aware of itching, annoying, sometimes disturbs sleep and daytime activities

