### 6.10.1 Local Skin Reactions (LSRs)

LSRs (telangiectasia, skin atrophy, striae rubrae, erythema, edema, scaling/dryness, stinging/burning, and pruritus) will be listed ([Listing 16.2.9.1](#)) and summarized by the frequency of each individual LSR by treatment group (CB-03-01 and Vehicle) and severity at each visit ([Table 14.3.5.1](#)).

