### 6.10.3 *Electrocardiograms (ECGs)*

ECGs will be evaluated for any material change during the study period. Overall interpretation (normal/borderline/abnormal) of the ECG will be listed (Listing 16.2.9.2) and summarised by treatment group (CB-03-01 and Vehicle) at each visit using contingency tables (Table 14.3.5.2). Values for heart rate, RR duration, PR duration, QRS duration, QT duration including Bazett's and Fridericia's corrections, P axis and their changes from baseline will be listed and summarised by treatment group (CB-03-01 and Vehicle) at each visit (Table 14.3.5.2) using descriptive statistics (mean, standard deviation, CV%, minimum, median and maximum). Changes in overall interpretation (normal/borderline/abnormal) of the ECG from Baseline to Visit 4 (Day 85 ± 10) will be examined using shift tables (Table 14.3.5.3).

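### For erythema, edema and scaling/dryness, the by-visit LSR table cannot separate acne signs that resolve from reactions that newly appear or worsen under the cream.

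*Protocol*

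**What the plan says.** Protocol 17.3.3.1 plans one summary of LSRs: they "will be summarized by the frequency of each individual LSR by treatment group and severity at each visit". SAP 6.10.1 has the same table, with LSRs "summarized by the frequency of each individual LSR by treatment group (CB-03-01 and Vehicle) and severity at each visit", and a listing by subject. Neither text mentions change from baseline, a shift table, a worst post-baseline grade or a count of subjects who worsened.

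Protocol 10.4 divides the eight LSRs into three groups:

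- Telangiectasia, skin atrophy and striae rubrae are "LSRs known to be associated with application of topical steroids".
- For erythema, edema and scaling/dryness, "the investigator or designee will evaluate the severity of the following LSRs known to be associated with acne vulgaris".
- Stinging/burning and pruritus are rated by the subject on four-point scales. The other six use five-point scales.

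Visit 1 has two LSR assessments (Protocol 9.1). The first is before the first dose: "Record Baseline LSRs (prior to application of the test article". The second is after it: "Record any AEs and LSRs (see Section 10.4) after the initial application of the test article". LSRs are scored again at Weeks 4, 8 and 12. Subjects who withdraw complete the Visit 4 procedures (Protocol 13.2).

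Under Protocol 10.4, a listed LSR becomes an AE only if it needs medical intervention or withholding of the test article.

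**The concern.** Every subject enters with at least 30 inflammatory and 30 non-inflammatory lesions (Protocol 5.1.1), so some are likely to have erythema, edema or scaling before any cream is applied. The trial is designed to show that the cream clears acne better than vehicle. For these three signs, the percentage affected at a later visit is the sum of two parts: disease signs that have not yet resolved, and signs that were absent at baseline and have appeared since. If the cream works, the first part shrinks more on active. If the cream also irritates, the second part grows more on active. The two movements offset each other in a cross-sectional table.

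Safety is part of the primary objective (Protocol section 3). Protocol 14.1 reports that earlier LSRs were mostly minimal to mild, with erythema the most frequent, and that only two AEs, both in one subject, were judged probably or possibly related to treatment. The AE tables may therefore carry little of the local-tolerability information, which leaves the by-visit LSR table as its main summary.

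**Working it through.** The documents state no LSR rate, so there is no planned figure to reproduce. The check asks whether offsetting can happen at plausible rates, and when it does not.

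**Inputs**

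- Resolution of baseline signs: rA = 0.37 on active and rV = 0.23 on vehicle. These are borrowed from the assumed percent changes in inflammatory lesions, -37 and -23 (Protocol 17.2). Using them as resolution rates for skin signs is an assumption.
- New onset on vehicle among subjects clear at baseline: nV = 0.05 (assumption).
- Baseline prevalence b, equal in both arms: 0.20 to 0.60 (assumption).
- Subjects per arm: 350 (Protocol 17.2).

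**Formulas**

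Week 12 prevalence = b(1 − r) + (1 − b)n.

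Setting the two arms equal and solving for active new onset: nA = nV + b(rA − rV)/(1 − b).

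Extra newly affected active subjects = 350 × (1 − b)(nA − nV) = 350 × b × 0.14.

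**Results**

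| b | nA giving equal prevalence | Week 12 prevalence, both arms | Extra subjects per 350 |
|---|---|---|---|
| 20% | 8.5% | 19.4% | 10 |
| 30% | 11.0% | 26.6% | 15 |
| 40% | 14.3% | 33.8% | 20 |
| 50% | 19.0% | 41.0% | 25 |
| 60% | 26.0% | 48.2% | 29 |

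Example at b = 0.50: vehicle 0.50 × 0.77 + 0.50 × 0.05 = 0.410; active 0.50 × 0.63 + 0.50 × 0.19 = 0.410. The by-visit difference is zero, while new onset is 19% against 5% of subjects clear at baseline.

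**When offsetting is absent or partial**

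- Equal clearing (23% in both arms), b = 0.30, new onset 11% against 5%: active 0.231 + 0.077 = 30.8%; vehicle 0.231 + 0.035 = 26.6%. The table shows 4.2 points, which is the whole excess (0.70 × 0.06 = 0.042). The offset therefore comes from differential clearing.
- Clearing 37% against 23%, b = 0.50, new onset 30% against 10%: active 0.315 + 0.150 = 46.5%; vehicle 0.385 + 0.050 = 43.5%. The table shows active 3 points worse, although the excess of new onset is 0.50 × 0.20 = 10 points of the arm. The direction is right and the size is understated.

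**The case against.** The strongest case for the plan has five parts.

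- **The table shows more than one number.** It covers each visit, including Baseline, by severity and arm, beside a randomised vehicle control. The net comparison is valid, each arm's starting distribution is visible, and cancellation at Week 12 need not occur at every visit or grade. The Visit 1 post-application score precedes any clearing. All this stands. But by-visit distributions do not show which subjects changed, and the post-application score reflects a single dose.
- **There is a listing, and the table shells may contain more.** The listing exists, but for 732 subjects (SAP 2.4) it is not a summary. The shells in SAP Appendix 1 are not in the documents available, so they cannot settle the point either way.
- **Worse irritation does reach the AE tables.** Protocol 6.3 tells subjects to stop use and contact the site if irritation or rash develops. Withholding makes the LSR an AE, and SAP 6.10.2 counts AEs that start or worsen after the first dose. This stands. What remains only in the LSR table is mainly irritation too mild to interrupt use.
- **The ECG comparison is weak.** ECG interpretation "from Baseline to Visit 4 (Day 85 ± 10) will be examined using shift tables", but ECGs are taken at only two visits, so that format is natural. Using another format for LSRs is not an inconsistency.
- **Baseline-referenced tables are not clean either.** They also count acne flares, which may be commoner on vehicle. This stands, and it is why they must be read against vehicle.

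A reader might infer that the planned table will show the cream as equal to or better than vehicle, or that all eight LSRs are masked. The documents support neither. They give no LSR rates, and the last calculation above shows active as worse. Only three LSRs are called acne-associated; the argument is not shown for the steroid-type signs, stinging/burning or pruritus.

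**Conclusion.** The point holds for erythema, edema and scaling/dryness. Their only planned summary cannot separate resolution of acne signs from new or worsened reactions, and milder reactions do not appear in the treatment-emergent AE tables.

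Under the stated assumptions, an excess in new onset of 3.5 to 21 percentage points among subjects clear at baseline can coexist with identical Week 12 prevalence. These sizes rest on assumed baseline prevalence, assumed vehicle new onset and a borrowed proxy for resolution. They show what is possible, not what is expected.

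The plan matches its own safety endpoint (Protocol 17.1.2, SAP 4.1.2), so this is about how informative the summary is and not a contradiction. No hypothesis test, error rate or data collection is affected. The change is still worth making, because it alters what can be concluded about local tolerability at very little cost.

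**What to change.** Keep the by-visit table. Add to Protocol 17.3.3.1 and SAP 6.10.1, by arm:

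1. A shift table from the pre-application Visit 1 grade to the worst post-baseline grade.
2. The number and percent of subjects with new onset (grade 0 at baseline) and with worsening by at least 1 grade, at any post-baseline visit including early termination.

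Do this at least for the three acne-associated signs, and for the other five LSRs for consistency. Define any severity cut-off separately by scale, because grade 3 is moderate on the five-point scales but severe on the four-point scales. Moderate or worse, for example, is 3 or higher on the former and 2 or higher on the latter. State that the pre-application score is the baseline, and show the Visit 1 post-application score separately.

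The tables reduce masking but do not remove it in subjects who already have the sign at baseline. Because they also count acne flares, the text should say that they are read against the vehicle arm.

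The cost is a short addition to each document and one or two table shells. The data are already collected, and sites and subjects have nothing more to do. SAP section 1 says the plan is finalised before database lock, so the tables can be specified while treatment is still blinded.
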